## 15.0 Drug Information

### 15.1 Pembrolizumab (MK-3475, SCH 900475, Keytruda®)

#### 15.11 Background

Pembrolizumab is a potent humanized IgG4 monoclonal antibody with high specificity of binding to the PD-1 receptor, thus inhibiting its interaction with PD-L1 and PD-L2. Based on preclinical *in vitro* data, pembrolizumab has high affinity and potent receptor blocking activity for PD-1.

#### 15.12 Formulation

Pembrolizumab is available as a liquid 25 mg/mL, 100 mg/vial.

#### 15.13 Preparation and storage:

Vials should be stored in the refrigerator at temperatures between 2-8°C. Drug concentrate is further diluted with normal saline (or 5% dextrose) in the concentration range of 1 to 10 mg/mL. The infusion solution in the IV bag should be immediately administered. Diluted pembrolizumab solutions may be stored at room temperature for a cumulative period of up to 6 hours. This includes room temperature storage of admixture solutions in the IV bags and the duration of infusion. The product can also be stored under refrigeration at 2°C to 8°C for no more than 96 hours from the time of dilution. If refrigerated, the diluted solution must be allowed to come to room temperature prior to administration. The solution must be discarded after 6 hours at room temperature or 96 hours under refrigeration.

#### 15.14 Administration

Pembrolizumab is administered by intravenous infusion over 30 minutes via a 0.22 micron in-line filter. The final infusion volume must be between 1 and 10 mg/mL. Maximum rate of infusion should not exceed 6.7 mL/minute through a peripheral or indwelling catheter. Flush the line with 0.9% NaCL following the completion of the infusion.

#### 15.15 Pharmacokinetic information:

- a) Absorption – Because pembrolizumab is administered intravenously, it is immediately and completely bioavailable. Steady-state concentrations of pembrolizumab are reached by 16 weeks of repeated dosing with a Q3W regimen and the systemic accumulation is 2.1-fold. The peak concentration, trough concentration, and area under the plasma concentration versus time curve at steady state of pembrolizumab increased dose proportionally in the dose range of 2 to 10 mg/kg Q3W.
- b) Distribution – Pembrolizumab has a limited volume of distribution.
- c) Excretion – CL is approximately 23% lower after achieving maximal change at steady state compared with the first dose. The terminal elimination half-life ( $t_{1/2}$ ) is estimated to be 22 days at steady state.
- d) Metabolism - Pembrolizumab is catabolized through non-specific pathways; metabolism does not contribute to its CL.

## 15.16 Potential Drug Interactions

There are no known significant drug interactions.

## 15.17 Known potential toxicities

Very common known potential toxicities,  $\geq 10\%$ :

Gastrointestinal disorders: diarrhea, nausea, abdominal pain

Skin and subcutaneous tissue disorders: rash, pruritis

General disorders and administration site conditions: fatigue

Common known potential toxicities,  $\geq 1\%$  to  $< 10\%$ :

Blood and lymphatic system disorders: anemia

Immune system disorders: infusion related reaction

Endocrine disorders: hyperthyroidism, hypothyroidism

Metabolism and nutrition disorders: decreased appetite

Nervous system disorders: headache, dizziness, dysgeusia

Respiratory, thoracic, and mediastinal disorders: pneumonitis, dyspnea, cough

Gastrointestinal disorders: colitis, vomiting, constipation, dry mouth

Skin and subcutaneous tissue disorders: severe skin reactions, vitiligo, dry skin, erythema

Musculoskeletal and connective tissue disorders: arthralgia, myositis, musculoskeletal pain, arthritis, pain in extremity

General disorders and administration site conditions: asthenia, edema, pyrexia, influenza like illness, chills

Investigations: alanine aminotransferase increased, aspartate aminotransferase increased, blood alkaline phosphatase increased, blood creatinine increased

Uncommon known potential toxicities,  $\geq 0.1\%$  to  $< 1\%$ :

Infusion related reactions

Blood and lymphatic system disorders: neutropenia, thrombocytopenia, leukopenia, lymphopenia, eosinophilia

Endocrine disorders: hypophysitis, adrenal insufficiency, hyponatremia, Thyroiditis, hypopituitarism

Metabolism and nutrition disorders: type I diabetes mellitus, hyponatremia, hypokalemia, hypocalcemia

Psychiatric disorders: insomnia, confusional state

Nervous system disorders: epilepsy, lethargy, peripheral neuropathy

Eye disorders: uveitis, dry eye

Cardiac disorders: myocarditis, atrial fibrillation

Vascular disorders: hypertension

Gastrointestinal disorders: pancreatitis, dysphagia

Hepatobiliary disorders: hepatitis

Skin and subcutaneous tissue disorders: lichenoid keratosis, psoriasis, alopecia, dermatitis, dermatitis acneiform, eczema, hair color changes, papule

Musculoskeletal and connective tissue disorders: tenosynovitis, myelitis

Renal and urinary disorders: nephritis, acute kidney injury

Investigations: blood bilirubin increased, amylase increased, hypercalcemia

Respiratory: pneumonia aspiration

Rare known potential toxicities,  $< 0.1\%$  (Limited to important or life-threatening):

Blood and lymphatic system disorders: immune thrombocytopenic purpura, hemolytic anemia

Immune system disorders: sarcoidosis

Nervous system disorders: Guillain-Barre syndrome, myasthenic syndrome, exacerbation of myasthenia gravis

Gastrointestinal disorders: small intestinal perforation

Skin and subcutaneous tissue disorders: toxic epidermal necrolysis, Stevens-Johnson syndrome, erythema nodosum

The risk profile for pembrolizumab also includes two important potential risks: a) myasthenic syndrome, and b) an increased risk of severe complications (such as early severe graft versus host disease and veno-occlusive disease) of allogeneic transplant in patients with hematologic malignancies who have previously been treated with PD-1 inhibitors.

Patients with multiple myeloma who were treated with pembrolizumab in combination with either pomalidomide or lenalidomide and dexamethasone, had an increased number of serious side effects and deaths as compared to patients who received only dexamethasone and either pomalidomide or lenalidomide. The benefit-risk profile is unfavorable for the combination of pembrolizumab, pomalidomide, and dexamethasone in relapsed refractory multiple myeloma, and the combination of pembrolizumab, lenalidomide, and dexamethasone in newly diagnosed treatment-naive multiple myeloma.

Post marketing reports identified Vogt-Koyanagi-Harada syndrome and hemophagocytic lymphohistiocytosis.

#### 15.18 Drug procurement

Pembrolizumab will be provided free of charge to study participants by Merck.

#### 15.19 Nursing guidelines

15.191 Pembrolizumab side effects vary greatly from those of traditional chemotherapy and can vary in severity from mild to life threatening. Instruct patients to report any side effects to the study team immediately. Side effects may be immediate or delayed up to months after discontinuation of therapy. Most side effects are reversible with prompt intervention of corticosteroids.

15.192 Diarrhea can be seen however is less common than that seen with anti-CTLA-4 agents. However it can be severe, leading to colonic perforation. Instruct patients to report ANY increase in the number of stools and/or change in baseline, blood in the stool, abdominal pain to the study team immediately.

15.193 Rash/pruritis/dermatitis is seen. Patients should report any rash to the study team. Treat per section 9.0 and monitor for effectiveness.

15.194 Monitor LFT's closely as elevations in these levels could indicate early onset autoimmune hepatitis. Patients should also be instructed to report any jaundice, or right upper quadrant pain to the study team immediately.

- 15.195 Pneumonitis can be seen and may be mild (only seen on imaging) to severe. Patients should be instructed to report any SOB, dyspnea, cough, chest pain, etc. to the study team immediately. Patients reporting these symptoms should have a pulse ox checked and consider immediate imaging per the treating MD.
- 15.196 Endocrinopathies (including hypopituitarism, hypothyroidism, hypophysitis, and adrenal insufficiency) are seen with this agent. Patients may present only with the vague sense of fatigue and “not feeling well”. Additional symptoms may be that of nausea, sweating and decreased activity tolerance. Instruct patients to report these signs or symptoms immediately and obtain appropriate labs as ordered by MD.
- 15.197 Patients who are started on steroid therapy for any side effects of pembrolizumab toxicity should be instructed to take the steroids as ordered, and not to discontinue abruptly as symptoms may return and be severe. Patients may be on steroid therapy for weeks. Instruct patients to report any increase or change in side effects with any dosage decrease as patients may need a slower taper.
- 15.198 Fatigue is common and may or may not be associated with immune related side effects. Assess patient’s fatigue level prior to each cycle of therapy and report any changes to the study team.
- 15.199 Patients should avoid receiving live DC within 30 days of study drug administration or per other study guidelines.
- 15.200 Patients who have undergone an allogenic bone marrow transplant, have an increased risk of severe complications including early GVHD, and venoocclusive disease, if they have previously been treated with pembrolizumab
- 15.201 Myocarditis has been reported and associated with pembrolizumab. Instruct patients to report chest pain, SOB, or dyspnea to study team immediately and/or seek emergency medical attention.
- 15.202 Autoimmune hematologic disorders including ITP and hemolytic anemia have been reported. Monitor blood counts closely and report any abnormalities to the study team.
- 15.203 Rare neurologic disorders including Guillian-Barre syndrome and myasthenia gravis have been reported. Instruct patients to report any neurologic symptoms including weakness, paresthesias or numbness, tingling to the study team immediately.

## 15.2 Dendritic Cells

- 15.21 Background: The DC used in this study is patient’s autologous dendritic cells (DC). Dendritic cells are cells manufactured in lab from monocytes removed from patients’ blood by leukapheresis. The dendritic cells need to acquire tumor antigens in order to stimulate anti-tumor immunity. Patients will be treated with DC placed into a tumor killed using cryoablation where tumor

antigen exposure will occur *in vivo*.

- 15.22. Formulation: DC is supplied as recently thawed cells prepared from patient material. Cells are manufactured and released by the Human Cellular Therapy Lab, Mayo Clinic Rochester. Before released for use, cells will undergo testing for sterility and potency.
- 15.23 Preparation and storage: DC will be prepared and stored at the Human Cellular Therapy Lab, Mayo Clinic Rochester according to approved SOPs included in the IND. The drug will be supplied to the appropriate administration area by personnel from the Human Cell Therapy Lab.
- 15.24 Administration: Each patient will undergo percutaneous cryoablation of the lymphoma tumor lesion to a cryoablated size of less than or equal to 2 cm in diameter equal to 50 – 75% of the index lymphoma lesion. Incomplete treatment of the index lymphoma tumor lesion will significantly minimize risk of thermal injury to adjacent structures, yet result in desired cytotoxic cell injury. Our general cryoablation technique has been previously described (Atwell, Farrell et al. 2008). Patients will be treated at on the 3W CT scanner. Due to the extended length of the procedure, requiring the patient to lie still (expected duration 45 minutes), sedation will be managed by the Department of Anesthesia. Using ultrasound guidance, a cryoprobe will be placed in the index lymphoma node. The node will be treated using a conventional freeze-thaw-freeze cycle with each freeze stage lasting 10 minutes or until the iceball reaches within 3mm of the outer node margin (as determined by CT monitoring at 2 minute intervals).
- Following the freezing procedure, the cryoprobe will be actively warmed and then withdrawn. After the node has thawed, a 22 G needle will be placed under ultrasound-guidance into the ablated portion of the node. The DC will be administered through this needle in 10 – 15 divided injections over different areas of the cryoablated region and then flushed with 1 ml of sterile saline.
- 15.25 Pharmacokinetic information: NOTE: this drug is a biologic made up of cells from the patient. Classical drug pharmokinetics do not apply.
- 15.26 Potential Drug Interactions: Unknown.
- 15.27 Known potential toxicities: Unknown.
- 15.28 Drug procurement: Drug is manufactured on site in the [REDACTED]

### 15.3 Pneumococcal 13-valent Conjugate Vaccine (Prevnar13)

- 15.31 Background: Pneumococcal 13-valent Conjugate Vaccine (Diphtheria CRM197 Protein), is a sterile solution of saccharides of the capsular antigens of *Streptococcus pneumoniae* serotypes 1, 3, 4, 5, 6A, 6B, 7F, 9V, 14, 18C, 19A, 19F and 23F individually linked to non-toxic diphtheria CRM197 protein. Each serotype is grown in soy peptone broth.

Potency of the formulated vaccine is determined by quantification of each of the saccharide antigens, and by the saccharide to protein ratios in the individual glycoconjugates.

- 15.32 Formulation: Supplied as ready-to-use prefilled syringes (10 x 0.5-mL prefilled syringes per package). Pneumococcal 13-valent Conjugate Vaccine is manufactured as a liquid preparation for intramuscular injection. Each 0.5 mL

dose of the vaccine is formulated to contain approximately 2.2 µg of each of *Streptococcus pneumoniae* serotypes 1, 3, 4, 5, 6A, 7F, 9V, 14, 18C, 19A, 19F, 23F saccharides, 4.4 µg of 6B saccharides, 34 µg CRM197 carrier protein, 100 µg polysorbate 80, 295 µg succinate buffer and 125 µg aluminum as aluminum phosphate adjuvant.

15.33 Preparation and storage: Pneumococcal 13-valent Conjugate Vaccine is stored at refrigerated temperatures of 2°C to 8°C (36°F to 46°F) away from freezer compartment. DO NOT FREEZE. Discard if frozen.

15.34 Administration: Shake vigorously immediately prior to use to obtain a uniform suspension in the vaccine container. The vaccine should not be used if it cannot be resuspended. After shaking, the vaccine is a homogeneous, white suspension. Do not mix the vaccine with other products in the same syringe.

The dose is 0.5 mL to be given intramuscularly. *Do not inject intravenously, intradermally or subcutaneously.* The vaccine should not be injected in the gluteal area or areas where there may be a major nerve trunk and/or blood vessel. Before injection, the skin at the injection site should be cleansed and prepared with a suitable germicide. After insertion of the needle, aspirate and wait to see if any blood appears in the syringe, which will help avoid inadvertent injection into a blood vessel. If blood appears, withdraw the needle and prepare for a new injection at another site.

15.35 Potential Drug Interactions: Patients receiving therapy with immunosuppressive agents (large amounts of corticosteroids, antimetabolites, alkylating agents, cytotoxic agents) may not respond optimally to active immunization.

As with other intramuscular injections, Pneumococcal 13-valent Conjugate Vaccine should be given with caution to patients on anticoagulant therapy.

See complete prescribing information for information regarding co-administration of Pneumococcal 13-valent Conjugate Vaccine with other vaccines.

15.36 Known potential toxicities: There is no safety data available in the adult patient population. Please see Prevnar13® prescribing information for comprehensive toxicity data.

The following systemic events were noted within 2-3 days of the Pneumococcal 13-valent Conjugate Vaccine injection in pediatric patients: fever, irritability, drowsiness, restless sleep, decreased appetite, vomiting, diarrhea, and urticaria-like rash. The following local reactions occurred within 3 days of immunization pediatric patients: erythema, induration, tenderness and interference with limb movement.

15.37 Drug procurement: Prevnar13 will be purchased with study funds and provided free of charge to patients.

15.38 Nursing Guidelines:

15.381 Monitor for injection site reaction. Local reaction is usually seen within 3 days of vaccination, including erythema, induration and tenderness. Treat symptomatically and monitor for signs on infection.

15.382 Patients may experience mild fever. Acetaminophen can be used symptomatically. Monitor for effectiveness.

15.383 Patients may experience “flu-like” symptoms (fever, irritability, decreased appetite, vomiting and diarrhea). Treat symptomatically.

## 16.0 Statistical Considerations and Methodology

### 16.1 Overview:

This is a phase I/II study of dendritic cell therapy and Pembrolizumab for patients with non-Hodgkin Lymphoma. The Phase I portion utilizes a 3+3 design with dose de-escalation only to identify the MTD of this treatment regimen. In this study, MTD means the maximum tolerated dose level/schedule. The Phase II portion is designed as an open-label study of patients having non-Hodgkin lymphoma.

#### 16.11 Primary Endpoint:

The primary endpoint of the phase I portion of this trial is to assess DLT to determine the maximum tolerated dose level/schedule (MTD). For the phase II portion of this trial the pembrolizumab primary endpoint is the clinical response of combination therapy with pembrolizumab, cryoablation and intra-tumor injection of autologous DC at MTD dose schedule.

A success will be defined as a confirmed response: PR or CR. Throughout Section 16.0, PR or CR will be considered synonymous with “success” in the phase II portion, unless specified otherwise.

#### 16.12 Sample Size

The phase I portion of this study is expected to require a minimum of 3 and a maximum of 12 evaluable patients. The 3 or 6 patients treated at the MTD in the phase I portion will also be included in the phase II portion.

A maximum of 28 additional evaluable patients will be accrued at the MTD dose level for a maximum of 34 evaluable patients in the phase II portion of this study. We anticipate accruing up to 4 additional patients (1 phase I, 3 phase II) to account for ineligibility, cancellation, major treatment violation, or other reasons. Therefore, a maximum of 13 patients will be accrued in the phase I portion and a maximum of 31 patients will be accrued to the phase II portion for an overall maximum of 44 patients for the entire study.

#### 16.13 Accrual Rate and Study Duration

The anticipated accrual rate is approximately 1-3 patients per month. Therefore, the accrual period for Phase I of this trial is expected to be approximately 12 months and for phase II to be approximately 22 months. If for any reason accrual fails to meet our expectations, we will pursue efforts to open this study at Mayo Clinic Scottsdale, AZ site. The maximum total study duration is expected to be approximately 4 years, or until the last patient accrued has been observed for at least 12 months.

### 16.2 Phase I Portion

#### 16.21 Study Design

The phase I study is designed to determine MTD and toxicity profile of dendritic cell therapy and pembrolizumab for patients with non-Hodgkin lymphoma using a 3+3 design with dose de-escalation only. Three patients will be treated at dose level 1 and observed for a minimum of six weeks (i.e. two full cycles and completion of Cycle 2 with pembrolizumab, cryoablation, and intra-tumor DC injection) before new patients are treated. Doses will not be escalated in any individual patient.

## 16.22 MTD Definition

MTD is defined as the dose level that does not induce DLT in at least one-third of patients (1 of 3 or 2 of 6 patients). A total of 6 patients treated at the MTD will be sufficient to identify common toxicities at the MTD. For instance, those toxicities with an incidence of at least 25% will be observed with a probability of at least 82% ( $1-(1-0.25)^6$ ). Refer to Section 7.61 for definition of DLT.

## 16.23 MTD Determination

The phase I portion of this study will follow dose levels and schedules as assigned in Section 7. The first cohort of three patients will be treated at dose level 1 and observed for 1 cycle of combination of Pembrolizumab, cryoablation, and intra-tumor DC injection (completion of Cycle 2) to assess toxicity. Decisions on when and how to dose de-escalate are described below.

16.231 If DLT (see Section 7.6) is not observed in any of the 3 patients, dose level 1 will be considered the MTD.

16.232 If DLT is observed in 1 of 3 patients treated at dose level 1, 3 additional patients will be enrolled and treated at the same dose level and evaluated after 1 cycle of combination therapy to assess toxicity.

If no additional DLT is observed, then dose level 1 will be considered the MTD.

If at least one additional DLT is observed in the new cohort of patients treated at dose level 1, then the next 3 patients will be treated at dose level -1.

i) If DLT is not observed in any of the 3 patients treated at dose level -1, then dose level -1 will be considered the MTD.

ii) If DLT is observed in 1 of 3 patients treated at dose level -1, then 3 additional patients will be treated at this dose level. If no additional DLT is observed in the new cohort of patients treated at dose level -1, then dose level -1 will be considered the MTD.

iii) If DLTs are observed in 2 or more of the 6 patients treated at dose level -1, then MTD will have been exceeded.

16.233 If DLT is observed in more than one of the 3 patients treated at dose level 1, then the next 3 patients will be treated at dose level -1. Decision rules for the 3 patients treated at dose schedule 2 follow 16.232 i) – iii) as described above.

16.234 If a patient fails to complete the first cycle of treatment for reasons other than toxicity, the patient will be regarded as inevaluable and will be replaced.

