  13. If an index tumor is amenable for excisional biopsy at Cycle 1 Day 1, then excisional biopsy may be performed at the discretion of the investigator. In this case, a separate index tumor will be identified for subsequent research biopsies.
  14. Cryoablation is performed on Day 2 of Cycle 2 only. If the previously identified tumor for cryoablation is decreased in size and can no longer be cryoablated, another tumor amenable to cryoablation will be identified for treatment. If no additional tumors can be identified for cryoablation, DC will be injected into the previously identified shrinking tumor.
  15. LDH performed on Day 1 of Cycles 4, 6, 8, 12, and 18.
  16. After Cycle 10, responsive or stable patients can be followed every other cycle by treating physician/provider until last cycle of treatment. However, patients will be followed by nurse at each cycle of treatment for adverse event assessment. They will be seen as needed by provider.
  17. If subject thyroid function tests are within normal at the end of treatment and have no clinical signs and symptoms of thyroiditis, thyroid function test does not need to be performed during active monitoring. If thyroid function tests are abnormal during treatment, these tests need to be followed until they return to normal.
  18. Retreatment starts at cycle 2.
  19. Every 3 months.
- R Research funded.

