### 7.112 Phase I dose level 1 schedule Treatment by Cycle

Cycle	Duration	Timepoint	Day
Cycle 1	3 weeks	Week 1 to Week 3	Day 1: Leukapheresis followed by pembrolizumab (DC manufacturing in lab)
Cycle 2	3 weeks	Week 4 to Week 6	Day 1: Pembrolizumab Day 2: Cryoablation  of tumor followed by intra-tumor injection of DC and injection of Prevnar13 in nearby region Day 8: DC as per section 7.115  Day 15: DC as per section 7.115 
Cycle 3	3 weeks	Week 7 to Week 9	Day 1: Pembrolizumab Day 2: Prevnar13, DC per Section 7.115  Day 8: DC per Section 7.115  Day 15: DC per Section 7.115 

Cycle	Duration	Timepoint	Day
Cycles 4 - 5	3 weeks		Day 1: Pembrolizumab Day 2: Prevnar13, DC as per Section 7.3 
Cycles 6 - 18	3 weeks		Day 1: Pembrolizumab Tumor biopsy on Day 1 of Cycle 6 only

1. If supply exhausted, start Cycle 6 of pembrolizumab.
2. If the previously identified tumor for cryoablation is decreased in size and can no longer be cryoablated, another tumor amenable to cryoablation will be identified for treatment. If no additional tumors can be identified for cryoablation, DC will be injected into the previously identified shrinking tumor.

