#### 7.16 Dose Limiting Criteria (DLT)

For this protocol, DLT will be defined as an adverse event attributed (definitely, probably, or possibly) to the study treatment during the first two cycles of treatment AND meeting the following criteria.

CTCAE System Organ Class	DLT Definition (CTCAE v4)
Investigations Neutrophil count decreased Platelet count decreased	≥Grade 4 ANC or PLT for ≥7 days
Infections and infestations Other, specify	Any ≥ Grade 3
Blood and lymphatic system disorders Febrile neutropenia	Defined as fever ≥38.5°C (38 >1 hour) with grade ≥4 neutropenia
Skin and subcutaneous tissue disorders Erythema multiforme Skin ulceration Urticaria	≥ Grade 3 erythema multiforme, ulceration, or urticaria that does not resolve to <Grade 2 within three weeks
Respiratory, thoracic and mediastinal disorders Bronchial obstruction Pneumonitis Wheezing	≥Grade 3 bronchial obstruction, pneumonitis, or wheezing
Immune system disorders Allergic reaction Autoimmune disorder	≥Grade 3 allergic reaction or autoimmunity
All Other Non-Hematologic	≥Grade 3 that does not resolve to < Grade 2 ≤ 72 hours per NCI Common Terminology Criteria for Adverse Events

Note: any adverse event that leads to a permanent discontinuation of the study agent is considered a DLT.

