## **8.0 Dosage Modification Based on Adverse Events**

### **8.1 Treatment schedule modifications in patients based on adverse events**

8.11 Patients will be evaluated by the study team prior to each dose of DC for an adverse event check. Determination will be made if the adverse event is treatment related (possible, probable or definite), i.e. a toxicity (see Section 10; Adverse event monitoring and reporting). If any adverse event has occurred, then the treatment schedule will be modified as in 8.12, 8.13, or 8.2. For cycles involving only pembrolizumab treatments (Cycles 1 and 6-18 for dose level 1 and Cycles 1 and 8-18 for dose level -1), refer to Section 8.2.

8.12 For Grade 1/2 adverse event during cycles with DC injections (Cycles 2 – 5 for dose level 1 and Cycles 2 – 7 for dose level -1): We will allow a delay in DC treatment up to four weeks for dermatological AEs  $\leq$  Grade 2; for all other Grade 1/2 adverse events not listed in Table 7.16 or 8.2, no change in procedure is required or expected.

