#### 16.241 Adverse Events / Toxicity Profile (Goal 2.1.11)

The primary endpoint of the phase I portion is the incidence of dose-limiting toxicity. A dose-limiting toxicity is defined in section 7.61. Toxicities will be assessed using the CTEP Active Version of the CTCAE. Non-hematologic toxicities will be evaluated via the ordinal CTC standard toxicity grading. Hematologic toxicity measures of thrombocytopenia, neutropenia, and leukopenia will be assessed using continuous variables as the outcome measures (primarily nadir) as well as categorization via CTC standard toxicity grading.

These data will be assessed in evaluating the tolerability of the regimen for future studies. All patients meeting the eligibility criteria who have signed a consent form and have begun treatment will be considered evaluable for dose-limiting toxicity. Incidence of DLT will be estimated by the number of patients with DLT divided by the total number of evaluable patients. No more than three patients will receive the first cycle of combination immunotherapy (Pembrolizumab and cryoablation and DC injections, i.e. Cycle 2 of the overall treatment plan) at any time during Phase I of the study.

For a comprehensive picture of toxicity profile, we will also summarize the incidence of other significant toxicities as defined in Section 8 or as a Grade 3 or higher adverse event otherwise not described in Section 8, that is possibly, probably, or definitely related to treatment. The number and severity of all adverse events (overall and by dose level) will be tabulated and summarized in this patient population. The Grade 3+ adverse events will also be described and summarized in a similar fashion. This will provide an indication of the level of tolerance for this treatment combination in this patient group. Frequency distributions, graphical techniques and other descriptive measures will form the basis of these analyses. Further longitudinal analysis techniques will be employed to explore the adverse event profile over time.

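### Phase I counts patients for DLT without requiring exposure to the combination: Sections 16.234 and 16.241 match neither each other nor the observation period in 16.21 and 16.23

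*Combined protocol and SAP*

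**What the plan says.** Four parts of the combined protocol and SAP bear on who counts for DLT in phase I.

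- **Window.** Section 7.16 counts treatment-attributed events "during the first two cycles of treatment AND meeting the following criteria".
- **Intended observation.** Section 16.23 has the first cohort "observed for 1 cycle of combination of Pembrolizumab, cryoablation, and intra-tumor DC injection (completion of Cycle 2) to assess toxicity". Section 16.21 says the same and sets a minimum of six weeks.
- **Replacement.** Under Section 16.234, if a patient "fails to complete the first cycle of treatment for reasons other than toxicity, the patient will be regarded as inevaluable" and is replaced.
- **Denominator.** Under Section 16.241, eligible and consented patients who "have begun treatment will be considered evaluable for dose-limiting toxicity". DLT incidence, the phase I primary endpoint, is DLT patients divided by that number.

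On treatment content, the Cycle 1 row in Section 7.112 reads "Day 1: Leukapheresis followed by pembrolizumab (DC manufacturing in lab"). Section 8.11 classes that cycle as pembrolizumab-only: "For cycles involving only pembrolizumab treatments (Cycles 1 and 6-18 for dose level 1". Footnote 14 of Section 4.1 states: "Cryoablation is performed on Day 2 of Cycle 2 only". The first DC dose is given on that same day. At dose level -1 both move to Cycle 2 Day 8 (Section 7.122).

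**The concern.** The regimen under test is the combination, and none of its added components is given before Cycle 2. The replacement rule looks only at the cycle before they start, and the denominator rule requires only that treatment has begun. No rule makes exposure to DC a condition for being counted. A patient who completes Cycle 1 and then withdraws, or for whom too few DC are available, is not replaced under 16.234. Absent a DLT, that patient counts as DLT-free under 16.241.

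The two sections also contradict each other. A patient who starts Cycle 1 and leaves before completing it for a non-toxicity reason is inevaluable under 16.234 and evaluable under 16.241.

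At stake are the phase I primary endpoint and the basis for the phase II schedule, which Section 7.5 takes from the phase I MTD.

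**Working it through.** **The plan's own phase I figure.** Section 16.22 gives 82% for seeing a toxicity of 25% incidence in 6 patients: 1 − 0.75^6 = 0.822. It reproduces. It presumes that all 6 were exposed to whatever causes the toxicity. For a toxicity arising only from the combination, with 5 exposed it is 1 − 0.75^5 = 0.763, and with 4 exposed 1 − 0.75^4 = 0.684.

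**Can an unexposed patient be counted?** Following one patient through the rules:

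1. Cycle 1 is completed, so 16.234 does not apply.
2. DC are insufficient, or the patient withdraws. Footnote 10 of Section 4.1, attached to Cycles 2 to 5, sends a patient with too few DC on to Cycle 6, which is pembrolizumab alone. A patient leaving for a reason other than an adverse event goes to event monitoring (13.9c), whose schedule in Section 4.4 lists no adverse event assessment.
3. The major-violation rule (13.9g) looks only at treatment in Cycle 1, so it does not catch this patient.
4. Section 16.241 counts the patient because treatment has begun.

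The plan itself allows for this: the feasibility ratio in 16.242 divides patients given at least one DC injection by patients leukapheresed.

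**Direction of the bias.** Let p be the DLT risk over Cycles 1–2 with the combination, q the risk without it, and u the share of counted patients who are unexposed. The expected DLT rate is (1 − u)p + uq. This is below p whenever q < p, that is, whenever the combination adds risk.

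**Illustrative size.** The documents give neither the true DLT rate nor the number unexposed, so both are assumptions. Under 16.231 and 16.232, dose level 1 becomes the MTD with 0 DLTs in the first 3 patients, or with 1 in 3 followed by 0 in the next 3.

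- All exposed: P = (1−p)^3 + 3p(1−p)^2 × (1−p)^3. At p = 0.33: 0.301 + 0.444 × 0.301 = 0.434.
- One of the first three unexposed with zero DLT risk, second cohort fully exposed: P = (1−p)^2 + 2p(1−p) × (1−p)^3. At p = 0.33: 0.449 + 0.442 × 0.301 = 0.582.

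The same two calculations at other true rates:

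| True DLT rate | All exposed | One of first three unexposed, zero risk |
|---|---|---|
| 25% | 0.600 | 0.721 |
| 33% | 0.434 | 0.582 |
| 40% | 0.309 | 0.464 |
| 50% | 0.172 | 0.312 |

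**Relaxing zero risk.** The unexposed patient did receive pembrolizumab, which can cause a DLT. Suppose one third to one half of the 33% arises in Cycle 1, so q = 0.11 to 0.165. Then P = (1−p)^2(1−q) + [2p(1−p)(1−q) + (1−p)^2 q] × (1−p)^3.

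- q = 0.11: 0.400 + 0.443 × 0.301 = 0.533.
- q = 0.165: 0.375 + 0.443 × 0.301 = 0.508.

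So 0.58 is the ceiling for one unexposed patient in the first cohort.

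**The case against.** The strongest reply is that the design already states the exposure it wants. Sections 16.21 and 16.23 describe a cohort observed to the end of Cycle 2 with the combination, and 16.232 evaluates the second cohort after one combination cycle. On that view 16.234 is loosely worded and its first cycle means the first combination cycle. This stands as evidence of intent, but not as a rule: none of those sentences says what happens to a patient who falls short. Where the plan means the combination cycle it names it, as in 16.241: "first cycle of combination immunotherapy (Pembrolizumab and cryoablation and DC injections, i.e. Cycle 2 of the overall treatment plan"). Reading 16.234 that way would also widen its conflict with the 16.241 denominator.

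It can also be said that 16.241 gives a descriptive rate within an analysis plan that 16.24 calls exploratory, while the MTD decision follows 16.23. That is fair, and it limits what 16.241 can do to the MTD. But 16.241 is where the phase I primary endpoint is defined and its denominator fixed.

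Two facts make the case less likely. Section 1.42 reports adequate vaccine for all 15 patients in the earlier trial using this manufacturing method, although 0 failures in 15 still has a one-sided 95% upper bound of 1 − 0.05^(1/15) = 18%. The second note in Section 11.0 keeps patients who progress before cryoablation on treatment if that is judged safe. Both narrow the gap; neither closes it.

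Phase II also has its own adverse event stopping rules (16.53), so its safety does not rest on the phase I count alone.

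**Conclusion.** The inconsistency is real and worth correcting. As written, the DLT denominator can include patients never exposed to the combination, and the phase I DLT rate is then biased down if the combination adds risk. On the stated assumptions, the chance of declaring dose level 1 the MTD rises from 0.43 to at most 0.58. That is an illustration conditional on one unexposed patient in the first cohort, not an estimate of what occurred.

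A reader might infer that dose level 1 was wrongly declared the MTD. The documents do not support that: they give no phase I exposure or DLT results and do not show that any counted patient missed DC. Nor do they give grounds for supposing that two of the first three were unexposed, which would be needed for a much larger distortion.

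Closed accrual does not remove the point. The DLT rate remains the phase I primary endpoint, and patients treated at the MTD also enter phase II (16.12).

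**What to change.** Give 16.234 and 16.241 one DLT-evaluable definition that matches 16.21 and 16.23. A patient is evaluable who either had a DLT in Cycles 1–2, or completed Cycle 2 having received pembrolizumab and at least one intratumoral DC injection. Cryoablation should be part of the requirement unless it was omitted under the protocol's own provision for patients with no ablatable lesion (footnote 14 of Section 4.1; footnote 2 of Section 7.112). An unconditional cryoablation requirement would drop patients treated as the protocol allows.

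Phase I closed to accrual on July 9, 2018, so no patient should be replaced. Instead:

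- report how many dose level 1 patients received cryoablation and how many received DC in Cycle 2; the 16.242 ratio covers DC only, and not by cycle;
- give the DLT rate in the exposed set beside the 16.241 rate, labelled as a post hoc per-exposure analysis.

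The cost is two sentences in Section 16 and one table. The downside is a possibly smaller denominator, with a wider interval. With no DLTs, for example, the one-sided 95% upper bound is 1 − 0.05^(1/3) = 63% for 3 patients and 1 − 0.05^(1/2) = 78% for 2.
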